3.1 Single center

Department of General Surgery and Center of Microinvasive Gastrointestinal Surgery, Southwest Hospital, China

3.2 Case group

Group A (Experimental): Robotic-assisted Total Gastrectomy with D2 Lymphadenectomy

Group B (Compared): Laparoscopic-assisted Total Gastrectomy with D2 Lymphadenectomy

3.3 Estimate sample size

This study is a non-inferiority study, with postoperative complications as primary outcome. According to the relevant studies, the postoperative complication rate of laparoscopic total gastric surgery is about 15%. In this study, it was assumed that the

postoperative complication rate of the study group was similar to the control group, with $\alpha=0.05$, $\beta=0.2$, and the non-inferiority threshold value set as 15%. PASS 11 was used for calculation, and the sample size of each group was 68 cases. Considering that the maximum detachment rate of this clinical study was 10%, the final sample size was 75 cases in each group.

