Outcome Measures	
Primary Outcome Measures :
 
 ● Overall postoperative morbidity rates 
Secondary Outcome Measures :
 
 ● Intraoperative morbidity rate ● Operative time ● Estimated blood loss ● Number of harvested and metastatic lymph nodes ● the lengths of incision, proximal and distal margins ● Time to first flatus ● Time to first liquid diet ● Postoperative hospital stay ● Total cost
Statistical considerations	
All data analyses will be performed using SPSS statistical software, version 23.0 (SPSS Inc), and the R software environment (R Foundation for Statistical Computing).
 
All data analyses will be conducted on a per-protocol (PP) basis. This study does not fill in missing values. Normally distributed continuous variables will be presented as mean and standard deviation and compared using the t-test if normally distributed, or as median and interquartile range and compared using the Wilcoxon rank-sum test if non-normally distributed; while categorical data will be presented as number and percentages and compared using the Pearson χ^2 test or the Fisher exact test, as appropriate. Sensitivity analysis is used for extreme outlier data. The confidence interval of the parameters is estimated with a 95% confidence interval. The central effect analysis and subgroup analysis are conducted according to the specific situation. All the statistical tests were tested by two sides. A p-value <0.05 is considered statistically significant.

1. Research background

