10.1 Statistical analysis plan

- Statistical software: we will use SPSS statistical software, version 23.0 (SPSS Inc), and the R software environment (R Foundation for Statistical Computing) to perform statistical analyses.
- Basic principle: The method of differential testing was adopted. The safety population of the study consists of the patients who receive safety evaluation data after the intervention. Descriptive statistics and two-sided tests were conducted for the safety indicators and the incidence of adverse reactions. A p-value <0.05 is considered statistically significant. The confidence interval of the parameters is estimated with a 95% confidence interval.
- Shedding analysis: Total shedding rate of two groups and loss rate due to adverse events will be compared using pearson χ^2 test

- All data analyses will be conducted on a per-protocol (PP) basis.
- Method of outlier determination: the observation value is greater than P75 or less than P25, and the exceed value more than 3 times of the quartile spacing ($=p75-p25$), which will be sentenced to outlier data. During the analysis, the sensitivity analysis is used for outlier data, namely analyzing outcomes including or excluding outlier's data. and if the results are not contradictory, the data is retained; if the contradiction, it depends on the specific circumstances.
- Descriptive statistics: The measurement data gives the mean, the standard deviation and the confidence interval, and the minimum value, the maximum value, the P25, the median and the P75 are given when necessary; matched data also gives the mean and standard deviation of the gap-value, and the median and average rank of the Non-parametric method. The nominal-scale data gives the frequency distribution and the corresponding percentages. The level data gives the frequency distribution and the corresponding percentages, as well as the median and the average rank. Qualitative data give positive rate, positive number, and denominator numbers. The survival data gives the number of events, the number of deletions, the median survival time, and the survival rate.
- Subgroup analysis : Sub-group analysis is to find the factors that may affect prognostic according to the specific circumstances of the data.
- Missing values handling: This study does not fill in missing values

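### The sample size of 68 per group fits a one-sided 5% test, but the protocol prescribes two-sided tests and 95% confidence intervals, under which power is about 69–70% rather than 80%

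*Protocol*

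**What the plan says.** Section 3.3 (repeated in the Summary) sets the design: "This study is a non-inferiority study, with postoperative complications as primary outcome". The control rate is put at about 15%, and the assumption for the robotic group is that the "postoperative complication rate of the study group was similar to the control group". Alpha is 0.05, beta is 0.2 and the non-inferiority threshold is 15%. The result is stated as "PASS 11 was used for calculation, and the sample size of each group was 68 cases", followed by "Considering that the maximum detachment rate of this clinical study was 10%, the final sample size was 75 cases in each group". Nothing in section 3.3 says whether alpha is one- or two-sided.

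The analysis rules stand elsewhere. The statistical considerations in the Summary say "All the statistical tests were tested by two sides", with p below 0.05 as the criterion. Section 10.1 says "The confidence interval of the parameters is estimated with a 95% confidence interval", and the Summary says the same. The protocol mentions no one-sided test and no 90% interval anywhere.

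**The concern.** A non-inferiority conclusion uses one side of the interval: the upper limit of the difference in complication rates (robotic minus laparoscopic) must lie below the margin. With a 95% two-sided interval, 2.5% is spent on that side. With a one-sided 5% test, or equivalently a 90% two-sided interval, 5% is spent there. The two rules need clearly different sample sizes. If the 68 was obtained under one rule and the analysis text prescribes the other, the stated 80% power does not belong to the planned analysis.

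This concerns the only primary outcome. A reader cannot tell whether the sponsor accepted a 2.5% or a 5% risk of wrongly declaring non-inferiority. With the interval level left open, a borderline result could be called either way after the data are seen.

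**Working it through.** **Inputs (all from section 3.3 unless noted).** Complication rate p = 0.15 in both groups, true difference 0; margin M = 0.15, read as absolute percentage points; power 80% (z = 0.8416); equal groups. Alpha is 0.05 with its side not stated, so both readings are tried: one-sided 0.05 (z = 1.6449), and one-sided 0.025 (z = 1.9600), which is what two-sided 0.05 or a 95% interval implies (Summary, section 10.1).

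**1. Closed formula (unpooled normal approximation).** n per group = (z_α + z_β)² × 2p(1 − p) / M², where 2p(1 − p)/M² = 0.255/0.0225 = 11.333.

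- One-sided 0.05: (1.6449 + 0.8416)² × 11.333 = 6.183 × 11.333 = 70.07, so 71.
- One-sided 0.025: (1.9600 + 0.8416)² × 11.333 = 7.849 × 11.333 = 88.95, so 89.

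**2. Reproducing 68.** The protocol names the software but not the test option. Exact binomial enumeration of the unpooled Z test at one-sided 0.05 gives power of 78.6% at n = 67 and 80.03% at n = 68. So 68 is the smallest size that reaches 80%, and the stated figure is recovered. At one-sided 0.025 the same enumeration gives 89.

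**3. Power at the planned sizes.** Normal approximation: power = Φ(M / √(2p(1 − p)/n) − z_α). At n = 68 the standard error is √(0.255/68) = 0.06124 and 0.15/0.06124 = 2.4495.

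- One-sided 0.05: Φ(2.4495 − 1.6449) = Φ(0.8046) = 78.9%.
- One-sided 0.025: Φ(2.4495 − 1.9600) = Φ(0.4895) = 68.8%.

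| | one-sided 0.05, normal | one-sided 0.05, exact | one-sided 0.025, normal | one-sided 0.025, exact |
|---|---|---|---|---|
| Power at 68 per group | 78.9% | 80.0% | 68.8% | 70.1% |
| Power at 75 per group | 82.3% | 82.4% | 73.0% | 73.0% |
| Smallest n for 80% | 71 | 68 | 89 | 89 |

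The loss at 68 per group is about 10 points by either method (80.0% to 70.1% exact; 78.9% to 68.8% normal).

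**4. Other test statistics.** The Farrington–Manning score test at one-sided 0.025 gives 65.5% (formula) or 67.0% (exact) at 68 per group, and its formula requires 95 per group for 80%. Continuity-corrected Z tests are lower still (59.9% exact at 68). No version at one-sided 0.025 comes near 68.

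**5. Attrition.** To keep 68 evaluable after 10% loss, 68/0.9 = 75.6, so 76 per group. The stated 75 leaves 75 × 0.9 = 67.5. It matches 68 × 1.1 = 74.8, which adds 10% instead of dividing by 0.9.

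**The case against.** The arithmetic behind 68 is sound once alpha is taken as one-sided. A one-sided 5% level is a legitimate choice for a directional hypothesis, and section 3.3 never calls its alpha two-sided. No sentence says that non-inferiority is to be judged on a 95% interval. The two-sided sentence in the Summary comes after a list of ordinary difference tests. Section 10.1 speaks of difference testing and of safety indicators, and its interval sentence is a general one. These could be reporting conventions, with the non-inferiority rule left to the separate SAP that section 10.1 mentions. The match to 68 also rests on an assumed exact method: the closed formula gives 71, and exact power is saw-toothed (79.6% at 69).

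Part of this stands. The 69–70% is conditional on judging non-inferiority by the 95% interval, and the software's method is inferred. The conflict remains all the same. The two-sided sentence covers all tests without exception, and 95% is the only interval level in the document. An SAP that used a 90% interval or a one-sided 5% test would contradict that text, and one that kept 95% would contradict the stated beta. Nor does the choice of method rescue 68, because every calculation at one-sided 0.025 requires at least 89. The attrition slip is real but amounts to one patient per group.

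**Conclusion.** The concern holds. The stated 80% power belongs to a one-sided 5% test that the protocol does not declare and that its analysis text contradicts. Under the 95% interval that the text does prescribe, power at 68 evaluable per group is 68.8% (normal) or 70.1% (exact), and somewhat lower with a score test. It is 73.0% even if all 75 per group are evaluable. Reaching 80% would take 89 evaluable per group.

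These figures rest on the protocol's own assumptions: 15% in both groups, an absolute 15-point margin, equal groups, and the upper limit of the 95% interval as the criterion. The fault lies in the undeclared and inconsistent level, not in the calculation that produced 68. The attrition shortfall is minor.

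**What to change.** Make the level consistent in the Summary, section 3.3 and section 10.1, choosing without reference to outcome data. Either:

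- state that alpha is one-sided 0.05 and that non-inferiority is judged on the upper limit of a 90% two-sided interval, exempt this comparison from the general two-sided and 95% statements, and keep 68; or
- keep the 95% interval as the criterion and restate power as about 69–70% at 68 evaluable per group.

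For attrition, state that 75 per group leaves about 67 evaluable at 10% loss. Raising the target to 76 would also correct the line, at one more patient per group, but is not essential.

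The cost is wording only. The first option openly accepts a one-sided error of 5% instead of 2.5%; the second replaces the power figure with a less favourable one. Neither requires added enrolment. Restoring 80% power under the 95% interval would need 89/0.9 = 98.9, so 99 per group, and is not proposed here.

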3.4 Blind method: This research adopts an open design

3.5 Research cycle

Estimated enrollment cycle: complete enrollment within 3 years

Follow-up period: begin at the enrollment of the first case and end 1 month after the enrollment of the last case.

Estimated time: 2018.01.08-2021.01.08(to complete enrollment)- 2021.02.08(to complete follow-up)

4. Study objects

All patients who meet the inclusion criteria and not conform to the exclusion criteria are qualified for this study.

4.1 Inclusion criteria

- (1) Age between 18 and 80 years
- (2) Endoscopic biopsy and CT confirmed locally advanced gastric adenocarcinoma, requiring D2 radical gastrectomy.
- (3) Preoperative examination showed no absolute contraindication and no distant metastasis
- (4) Performance status of 0 or 1 on ECOG scale
- (5) ASA class I, II, or III
- (6) Written informed consent

4.2 Exclusion criteria

- (7) Enlarged or bulky regional lymph node (diameter over 3cm) supported by preoperative imaging including those surrounding important vessels
- (8) Emergency surgery due to complication (bleeding, obstruction or perforation) caused by gastric cancer
- (9) Previous upper abdominal surgery(exceptlaparoscopic cholecystectomy)
- (10) Previous neoadjuvant chemotherapy or radiotherapy
- (11) Unstable myocardial infarction, angina, or cerebrovascular accident within the past 6 months
- (12) FEV1 < 50% of predicted values
- (13) Other malignant diseases

- (14) Severe mental disorder
- (15) Women during breast-feeding or pregnancy

4.3 Withdraw criteria

- (16) Patients intraoperatively/postoperatively confirmed as T4b
- (17) M1 tumor confirmed intraoperatively or postoperatively: distant metastasis only found by intraoperative exploration or postoperative pathological biopsy or a positive postoperative peritoneal lavage cytology examination
- (18) Requirement of simultaneous surgery for other diseases
- (19) Patients intraoperatively confirmed as unable to complete D2 lymph node dissection/R0 resection due to tumor: unable to complete R0 resection due to regional lymph node integration into a mass or surrounded with important blood vessels, which cannot be resected
- (20) Sudden severe complications during the perioperative period (intolerable surgery or anesthesia), which renders it unsuitable or unfeasible to implement the study treatment protocol as scheduled
- (21) Patients who voluntarily quit or discontinue treatment for personal reasons at any stage after inclusion in this study
- (22) Treatment implemented is proven to violate study protocol.

5. Outcome Measures

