
to conduct clinical research on robotic-assisted radical gastrectomy with D2 lymphadenectomy for locally advanced gastric cancer. At present, there is no prospective study report on the treatment of locally advanced gastric cancer with robot and laparoscopic D2 lymph node dissection.

Our center reported the first robotic-assisted gastrectomy in China in 2010, and has completed more than 600 cases of robotic-assisted gastrectomy. At present, there is a lack of prospective research literature reports on robot and laparoscopic radical total gastrectomy combined with D2 lymphadenectomy in the treatment of locally advanced gastric cancer, and the safety and effectiveness of robotic and laparoscopic radical total gastrectomy with D2 lymphadenectomy for locally advanced gastric cancer are still unclear. This study intends to conduct the first international prospective study of robot and laparoscopic radical total gastrectomy with D2 lymphadenectomy for the treatment of locally advanced gastric cancer, and to provide evidence-based medicine for the widespread development of robot-assisted total gastrectomy for locally advanced gastric cancer.

2. Objective

The purpose of the prospective trial is to investigate the safety and feasibility between Robotic and laparoscopic radical total gastrectomy with D2 lymphadenectomy for locally advanced gastric cancer.

3. Research design

prospective, single-center, non-randomized, controlled, non-blind, and non-inferiority observation trial

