9.2 Preoperative management

- In case of any deterioration of the clinical conditions from the selection time to the expected day of surgery, whether to undergo an elective surgery as planned should be decided in accordance with the judgment of the doctor in charge; if an emergency surgery is required, the case should be withdrawn from PP set according to Withdrawal Criteria;
- For patients with nutritional risks, preoperative enteral/parenteral nutritional support is allowed.
- For elderly, smokers, high-risk patients with diabetes, obesity, and chronic cardiovascular/cerebrovascular or thromboembolic history, among others, perioperative low-molecular-weight heparin prophylaxis, lower-limb antithrombotic massage, active lower limb massage, training in respiratory function, and other preventive measures are recommended. For other potentially high-risk complications not specified in this study protocol, the doctor in charge can decide on the most appropriate approach according to clinical practice and should record it in the CRF.
- For the operative approach of the surgeries in this study should be selected by the doctor in charge according to his/her experience and the specific intraoperative circumstances.
- Preoperative fasting and water deprivation and other before-anesthesia requirements on patients should follow the conventional anesthesia program, which is not specified in this study.
- For prophylactic antibiotics, the first intravenous infusion should begin 30 minutes before surgery. It is recommended to select a second-generation cephalosporin (there are no provisions on specific brands in this study); the preparation, concentration, and infusion rate should comply with routine practice; and prophylaxis should not exceed postoperative 24 hours (special case can be extended to 48 hours) at a frequency of one infusion every 12 hours. If a patient is allergic to

cephalosporins (including the history of allergy or allergy after cephalosporin administration), other types of antibiotics are allowed according to the specific clinical situation and when used over the same period mentioned.

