9.3.2 Operative parameters (same for both groups)

Completed by the research assistant on the day of the operation. specific projects include:

- (1) Name of responsible surgeons
- (2) Operation time (min)
- (3) Type of operation, digestive tract reconstruction, intraoperative damage and whether the tumor was ruptured during surgery (intact rupture of the capsule)
- (4) Length of incision (cm)
- (5) Conversion to open surgery or not and the reasons for this decision
- (6) Intraoperative estimated blood loss (ml; from skin cutting to stitching, intraoperative blood loss = (postoperative gauze weight, grams - preoperative gauze weight, grams) *1ml/g+ suction fluid, ml)
- (7) Blood transfusion (ml): in this study, the blood transfusion event is defined as transfusion of red cell suspension (ml) or whole blood (ml)
- (8) Tumor location
- (9) Tumor size (maximum tumor diameter, mm)
- (10) Number of lymph nodes dissected in each group and distant metastasis (location)
- (11) Proximal resected margin (mm), distal resected margin (mm), radicality(R0/R1/R2)
- (12) Intraoperative complications (occurring from skin incision to skin closure) including:

surgery-related complications: intraoperative hemorrhage and injury: A. Vascular injury: A vascular injury is defined as a blood vessel with either a blood vessel clamp or a titanium clamp closure and an intra-cavity suture or any other method to control the bleeding. B. Organ damage: maybe including diaphragmatic injury, esophageal injury, duodenal injury, colon injury, small intestine injury, spleen injury (excluding <1/3 spleen ischemia), liver injury, pancreatic injury, gallbladder injury, kidney damage etc.

C. Tumor rupture: tumor envelope Integrity damage

air abdominal-related complications: high-blood carbonate, mediastinal emphysema, subcutaneous emphysema, air embolism, respiratory circulation instability caused by abdominal pressure.

Anesthesia-related complications: Allergic reactions.

(13) Intraoperative death (occurring during the time period from skin cutting to skin stitching completion) regardless of reason.

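### Feasibility is an objective, but conversion, R0 resection and D2 completion are not outcomes, and the per-protocol rule removes tumour-related D2/R0 failures from analysis

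*Protocol*

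**What the plan says.** - **Objective (section 2).** "The purpose of the prospective trial is to investigate the safety and feasibility between Robotic and laparoscopic radical total gastrectomy with D2 lymphadenectomy".
- **Outcomes (5.1, 5.2).** The primary outcome is overall postoperative morbidity. The secondary list covers intraoperative morbidity, operative time, blood loss, node counts, incision and margin lengths, recovery times, hospital stay and cost. Conversion, R0 rate and D2 completion are absent.
- **Data collected (9.3.2).** Item (5) records "Conversion to open surgery or not and the reasons for this decision"; item (11) records radicality as R0, R1 or R2.
- **Withdrawal (4.3).** Criterion (19) covers "Patients intraoperatively confirmed as unable to complete D2 lymph node dissection/R0 resection due to tumor". It goes on to describe nodes fused into a mass or around major vessels that cannot be resected. Criterion (20) covers sudden severe perioperative complications, "which renders it unsuitable or unfeasible to implement the study treatment protocol as scheduled". Criterion (22) reads "Treatment implemented is proven to violate study protocol".
- **Analysis set.** Section 10.1 and the summary state: "All data analyses will be conducted on a per-protocol (PP) basis". Section 9.3.1.11 removes patients found during the operation to meet an exclusion from that set. Section 10.1 also names a safety population, and sections 8.1 and 8.2 calculate complication and mortality proportions over all operated patients.
- **Approach.** Section 3.2 defines the groups by type of operation. Section 9.2 says that the operative approach is to be "selected by the doctor in charge according to his/her experience and the specific intraoperative circumstances".

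**The concern.** Feasibility of a surgical approach is largely a question of whether the planned operation could be completed as planned. The protocol collects part of that information but does not list it as something to be compared. Its withdrawal criteria and per-protocol rule then take some of the failures out of the analysed set.

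Two things are at stake. First, a difference between the arms in completion of D2/R0 resection could exist and not appear in the analysed set. Second, patients withdrawn after severe complications may be the ones who would count against an approach on the primary outcome. Section 8 would count them and section 10.1 would not.

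A related gap is group membership. The study is not randomised, and no rule says whether the planned or the performed approach defines the group if the approach changes during surgery.

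**Working it through.** **1. The plan's own figures.** Inputs from section 3.3: 15% complications in each arm, 15-point margin, α = 0.05, power 80%. Exact binomial enumeration of the unpooled Z test at one-sided 0.05 gives power 0.8003 at 68 per group, so the stated 68 reproduces. For dropout, 68 × 1.1 = 74.8, rounded to 75 (68 / 0.9 = 75.6 would give 76). The sample size is not at issue here. The plan leaves room to lose 75 − 68 = 7 patients per arm, or 7/75 = 9.3%.

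**2. What happens to each kind of feasibility event.**

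| Event | Recorded? | Listed outcome? | In per-protocol set? |
|---|---|---|---|
| D2/R0 not possible because of tumour | radicality yes; no D2-completion item | no | no, criterion (19) |
| Severe complication making study treatment unfeasible | yes, as a complication | only as morbidity | no, criterion (20) |
| Conversion to open | yes | no | yes, unless another criterion applies |
| Robotic to laparoscopic switch | no item listed | no | not stated; could be read as (22) |
| Technical D2 failure, or R1 found at pathology | radicality yes | no | not removed by (19) |

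**3. Completion in the analysed set.** Let f be the share of started operations in an arm that fail D2/R0 because of tumour, and N the number started.

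- Completion with respect to tumour-related failure over all started operations: 1 − f.
- The same in the per-protocol set: N(1 − f) / N(1 − f) = 100% for any f below 1.

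If all 7 allowed losses in one arm were of this kind, true completion would be 68/75 = 90.7% and per-protocol completion 68/68 = 100%. With assumed rates of 2% and 10% (1.5 and 7.5 expected failures in 75), true completion would be 98% against 90%, and per-protocol completion 100% in both arms.

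**4. The primary outcome.** Let w be the share of operated patients withdrawn under criteria (19), (20) and (22), and c their complication rate. The rest are taken at the planned 15%.

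- All-operated rate = (1 − w) × 0.15 + w × c.
- Shortfall of the per-protocol rate = w × (c − 0.15).

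| w (assumed) | c (assumed) | All-operated rate | Per-protocol rate | Shortfall |
|---|---|---|---|---|
| 5% | 30% | 15.75% | 15% | 0.75 points |
| 5% | 100% | 19.25% | 15% | 4.25 points |
| 10% | 30% | 16.5% | 15% | 1.5 points |
| 10% | 100% | 23.5% | 15% | 8.5 points |

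These are shortfalls within one arm. The difference between arms is distorted only so far as w or c differs between them; equal withdrawals of equal risk would cancel.

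**5. Group membership.** Section 3.2 names the operation, not the plan. Section 9.2 allows intraoperative circumstances to influence the approach. Section 9.3.2 (5) records conversion to open only. A robotic start finished laparoscopically could therefore stay in Group A, move to Group B, or leave as a violation, and nothing in the text decides between these.

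**The case against.** A reader might infer that the feasibility objective cannot be answered at all, or that both operations must look feasible by construction. The text does not go that far, for these reasons.

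- **Criterion (19) is narrow.** It concerns tumour that cannot be resected and sits beside T4b and M1. It does not remove technical failure of D2 dissection or positive margins found at pathology. Nothing in the documents suggests that unresectability differs by approach.
- **Conversion to open is kept.** No withdrawal criterion names it. Section 9.3.1.12 defines it as an incision over 10 cm, and incision length is a secondary outcome, so it can be derived.
- **Per-protocol is not the only population named.** There is a safety population, and section 8 uses all operated patients.
- **Other indicators remain.** Operative time, blood loss, intraoperative morbidity, node counts and lengths can all differ between arms.
- **Losses are compared.** Section 10.1 tests total dropout and dropout due to adverse events between groups, and a breakdown by reason could sit in the analysis plan, which is not shown.
- **Switches are not described.** The documents mention no robotic to laparoscopic change and no rate. The section 9.2 sentence is ambiguous and stands under preoperative management.

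All of this limits the point, and three things survive it. Section 8's denominators do not cover conversion or completion, and they contradict the rule that all analyses are per-protocol. Comparing incision lengths is not comparing conversion proportions; section 9.3.1.2 also permits a longer auxiliary incision with reasons recorded, while section 9.3.1.12 counts any incision over 10 cm as a conversion. The dropout comparison mixes D2/R0 failure with T4b, M1, concurrent surgery and voluntary exit.

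**Conclusion.** The point holds for part of the feasibility objective. Without any assumed rate, the documents fix tumour-related D2/R0 completion at 100% in both arms of the per-protocol set, and they list no outcome for conversion, R0 or D2 completion. Some complication-driven failures may also be lost through criterion (20), and changes of approach through criterion (22); how many depends on how those criteria are applied.

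The effect on the primary outcome is an illustration only: 0.75 to 8.5 points within one arm, against a 15-point margin, if 5–10% are withdrawn and 30–100% of them have complications. It reaches the comparison only if withdrawals differ between arms. It would be wrong to conclude that the trial says nothing about feasibility or that conversions vanish from the data. The change is worth making because it is cheap and removes a selection effect from a stated objective.

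**What to change.** Add two secondary outcomes to section 5.2:

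- conversion from the planned approach (robotic to laparoscopic, or either to open), with the reason;
- R0 resection and D2 completion by the planned approach.

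Calculate both over all patients in whom the operation was started, grouped by the approach planned before surgery, alongside the per-protocol analysis. Do not drop from them patients who meet (19), (20) or (22), or whose approach changed. Report withdrawals by criterion and arm. Reconcile the denominators in sections 8.1 and 8.2 with the per-protocol rule in section 10.1, and state that the planned approach defines the group for these two outcomes.

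The cost is three small CRF items. Section 11.1.1 has an enrolment form due one day before surgery but does not say that it records the planned approach, so that must be added. A robotic to laparoscopic switch item and a D2-completion item are also needed, because section 9.3.2 lists neither. Conversion to open and radicality are already collected. The sample size and clinical management do not change. Reported success rates would be slightly less favourable.
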